Our proposed study seeks to shift the paradigm for promoting diet intake and physical activity using education and self-report to provide a powerful combination of mHealth dietary app and health coaching (set goals, provide ongoing feedback, and self-monitor behaviors). To our knowledge, this is the first time a mHealth dietary app and health coaching intervention has been used in kidney transplant recipients to link real-time data for monitoring dietary intake and physical activity.

The long-term goal of this work is to enhance well-being in kidney recipients via lifestyle self-management of care for dietary intake and physical activity to ultimately prevent chronic diseases. The proposed study is important because early weight gain after kidney transplant is associated with adverse effects on the transplanted kidney function resulting in increased health care cost and poor quality of life.⁷ Interventions are needed to monitor kidney transplant recipients diet and physical activity in real-time to prevent health decline.

The goal of the proposed feasibility study is to recruit a sample (N = 20) of post-kidney transplant recipients (age 18 and above) who will receive the mHealth dietary app + health coaching intervention for 12 weeks. We will assess changes over time for the primary outcome and secondary outcomes from baseline to 4, 8, and 12 weeks. We plan to submit our findings for publication to the Journal of Progress of Transplantation (Impact factor 0.958) or Trends in Transplantation (Impact factor 0.1.69). We *hypothesize* that the mHealth dietary app + health coaching intervention will improve adherence for recording diet and physical activity, decrease perceived stress, increase exercise self-efficacy, increase vegetable intake, decrease fat intake, decrease carbohydrate intake, improve weight control, improve blood pressure control, improve heart rate and an increase the number of minutes of physical activity per day. We will

also examine biological differences among the secondary outcomes of perceived stress, exercise self-efficacy, vegetable intake, fat intake, carbohydrate intake, weight, blood pressure, heart rate and minutes of physical activity per day, as previous studies have reported differences in outcomes based on age, sex, and race.^{8,9} The rationale for our hypothesis is that progression of cardiovascular disease and chronic disease may be slowed with daily tracking of dietary and physical activity.

II. Procedures

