Participant **Demographic Information** (10 minutes) will be obtained using a seven-item questionnaire demographics form and **Comorbidity Data** will be gathered using the Charlson Comorbidity Index³³ to describe the patient population. **Aim 1: Recruitment** (percent approached),

will be recorded in REDCap by the RA. **Retention** (percent dropped) will be recorded in REDCap by the RA. **Adherence** (percent to adhere to logging daily dietary intake and physical activity) will be recorded continuously each day by the “Lose-It” app. **Aim 2: Perceived Stress** (10 minutes) will be evaluated by using the Perceived Stress Scale (PSS).³⁵ The PSS is a 10-item questionnaire using a Likert Scale to rate feelings of stress from 0 “never” to 4 “very often.” The PSS has demonstrated excellent test-retest reliability (intraclass correlation coefficient = 0.954) and internal consistency (Cronbach's alpha = 0.810) with adults who have chronic disease.³⁶ **Exercise Self-Efficacy** (10 minutes) will be evaluated by using the Self-Efficacy for Exercise (SEE) Scale. The SEE is a 9-item questionnaire using a Likert Scale to rate feelings of stress from 0 “not confident” to 10 “very confident.” The SEE has demonstrated excellent internal consistency ($\alpha = 0.92$) for adults living with chronic disease.³⁷ **Vegetable intake** will be measured using the Block Fruit-Vegetable-Fiber Screener. The Block Fruit-Vegetable-Fiber Screener (5 minutes) has demonstrated high reliability (Spearman r -value of 0.71).³⁸ This brief screening tool includes seven questions about fruit and vegetable intake and three questions about foods high in fiber, magnesium, and potassium. **Fat Intake and Carbohydrate Intake** (5 minutes) will be recorded each day by the participant using the “Lose-It” app. **Weight** will be measured each day by the participant using a wireless Wi Fi weight scale. The data from the wireless weight scale will sync the data from the participant's mobile phone to the premium password-protect “Lose-It” database each day. **Blood Pressure and Heart Rate** will be recorded each day by the participant using a wireless Wi Fi blood pressure cuff. The data from the wireless cuff will sync from the participant's mobile phone to the premium password-protect “Lose-It” database each day. **Minutes of Physical Activity per Day** will be recorded each day by the participant using the “Lose-It” app. **Clinical Frailty Scale** (5 minutes) will be used to measure the frailty level of each participant. The screening tool has demonstrated high reliability in adults. This brief screening tool consist of nine questions about a person's level of frailty.

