
D. Detailed study procedures

The “Lose-It” app will be set up with Gmail accounts with unique unidentifiable codes developed by the research team. Participants will be instructed how to download the “Lose-It” app virtually using Zoom. In addition, participants will be taught how to sync to their smartphone and retrieve data from their app. The participants will be trained to enter their dietary intake and physical activity daily for 12-weeks.

Participants will monitor their vegetable intake, fat intake, carbohydrate intake, weight, blood pressure, heart rate and the minutes of physical activity per day using the “Lose-It” app. Wi-Fi connected weight scales and blood pressure cuff will be supplied for weight and blood pressure monitoring. Participants will be taught how to sync the data from the scales and blood pressure cuff to the “Lose-It” app using the Premium database which will Sync all of the data into password protected database for the research team to access. Participants will perform a return demonstration to confirm that they can record their dietary intake daily, physical activity, weight, and blood pressure using the “Lose-It” app. We also review with the participant the “My Plate” method for proper nutrition and the steps to distance conversion chart. Each participant will be given a copy of both via email.

Session	mHealth App + Health Coaching Intervention Setting: Online video- conference call (Zoom)
Baseline Session (Session 1)	The research assistant (RA) will demonstrate proper “Lose-It” app use, set up the smartphone application, and how to enter their dietary intake, physical activity, weight, blood pressure, heart rate and the minutes of physical activity per day using the “Lose-It” app. The RA will demonstrate how to sync the data from the Wi Fi weight scales and blood pressure cuff to the “Lose-It” app.
Time for session: 90 minutes	Participants will perform a return demonstration to confirm that they can access the “Lose-It” app, sync the data from the Wi Fi scales and blood pressure cuff.

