Week 1-12 (Sessions 2-13) Time for session: 30 minutes	
Phase 1: The participant will place the goals (dietary and physical activity) into their “Lose-It” app via smartphone for goal attainment.
 
Phase 2: The participant and the RA will review the electronic report generated from the “Lose-It” app for monitoring or assessing progress for dietary intake and physical activity each week from baseline to week 12.
 
Phase 3: The RA will review with the participant each week for 12 weeks how many days they implemented and achieved the solution for their daily goals.
 
Phase 4: Time will be allowed for any questions.

Risk and Benefits

The risks for harm to you for participating in this study are minimal. You may feel uncomfortable about having the research team knowing about your dietary intake or physical activity level. It is not unusual for people with a transplant to occasionally have difficulty with being physically active and controlling their weight. We are trying to help people with these common problems.

If you agree to take part in this study, there may or may not be direct medical benefits to you.

We hope the information learned from this study will in the future benefit other patients with a kidney transplant who are having difficulty becoming physically active and assessing their dietary intake.

E. Internal Validity

In the previous K award²² study, we found that the primary reason for participants not enrolling (65%) into the study was due to the distance of traveling to the research site. Thus, there is a need to deliver the intervention activities in home settings via Zoom. The delivery of our study research activities is timely due to the Coronavirus (COVID-19) and the fact that our population is immunocompromised. Due to the recent pandemic outbreak of the coronavirus (COVID-19) and since our population is immunocompromised. We will promote sustainability for participating in the study by sending weekly text messages to the participants to thank them for their participation in the study. The conduct of this feasibility study will help identify other limitations to consider for future studies in a larger multisite clinical trial. We will collect data regarding the time spent on delivering the intervention so that we can conduct a cost-effective analysis at a later date.

F. Data Analysis

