Descriptive statistics will be used to summarize sample characteristics. **Aim 1)** percent approached, percent dropped, and percent to adhere to logging daily dietary and physical activity will be analyzed using means and standard deviations of these variables and analyzed as differences between the baseline and 3-month measurements using the Wilcoxon Signed-Ranked test. **Aim 2)** Perceived Stress Scale, Exercise Self-efficacy Scale, Fruit, Vegetables, and Fiber Screener, fat intake, carbohydrate intake, weight, blood pressure, heart rate, and the minutes of physical activity per day will be analyzed using the differences among baseline, 4, 8, and 12 weeks using repeated measures analysis of variance using the Friedman's Test. Frailty levels will be collected at baseline and 12 weeks and will be analyzed using means and standard deviations of this variables. **Missing Data:** We will carefully record and code various reasons for missing data (e.g., participants forgot to record data into the "Lose-It" app) and examine the pattern of missing data.

III. Bibliography

2. Aksoy N. Weight Gain After Kidney Transplant. *Exp Clin Transplant.* 2016;14(Suppl 3):138-140.

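### The only Aim 2 test drops, outcome by outcome, anyone missing one of four time points, and six of the nine outcomes have no described measurement route once a participant stops the app

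*Combined protocol and SAP*

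**What the plan says.** Section I sets the goal to "recruit a sample (N = 20) of post-kidney transplant recipients", all of whom receive the intervention, and adds: "We will assess changes over time for the primary outcome and secondary outcomes from baseline to 4, 8, and 12 weeks". Section II.F then says that the Aim 2 outcomes "will be analyzed using the differences among baseline, 4, 8, and 12 weeks using repeated measures analysis of variance using the Friedman's Test". There are nine: perceived stress, exercise self-efficacy, the fruit, vegetable and fibre screener, fat, carbohydrate, weight, blood pressure, heart rate and activity minutes.

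On incomplete data, II.F says "We will carefully record and code various reasons for missing data" and that the pattern will be examined. It defines no analysis set, no available-data method, no imputation and no sensitivity analysis.

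On measurement, II.C has fat, carbohydrate and activity minutes entered daily in the app, and weight, blood pressure and heart rate taken daily on supplied devices that sync to the app's database. II.D agrees: "Participants will monitor their vegetable intake, fat intake, carbohydrate intake, weight, blood pressure, heart rate and the minutes of physical activity per day using the" app. That list also includes vegetable intake, but the vegetable outcome analysed in II.F is the screener. The contacts that handle data after baseline are the weekly coaching sessions, where "The RA will review with the participant each week for 12 weeks how many days they implemented and achieved the solution for their daily goals". II.E adds weekly thank-you texts, which collect nothing.

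**The concern.** The app is both part of the intervention and the measuring instrument for six outcomes. The plan does not distinguish stopping the app or coaching from leaving the study, and describes no measurement after someone stops. The named test then needs a full set of four values. Someone who gives values at baseline, week 4 and week 8 and stops at week 9 contributes nothing to the test of that outcome.

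What is at stake is who the Aim 2 results describe. Section I states its hypotheses of improvement for recipients given the intervention, whereas the tests would describe those with no gap at any of the four times. With one arm, no control group shares the same selection and offsets it. The plan itself expects losses: retention is a primary outcome, and II.F gives forgetting to record as an example of missing data.

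**Working it through.** The sample size of 20 comes with no power, precision or dropout calculation, so there is no figure of the plan's to reproduce. All missingness rates below are assumptions, because the documents give none.

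1. **Behaviour of the test.** In a check on artificial data (20 people, 4 times, 80 values) with one value missing, Friedman's test returned no result. With omission allowed, it gave chi-square 1.295, p = 0.730, identical to deleting that person. So 19 people were used and three observed values were lost.

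2. **People left, independent gaps.** With baseline observed and probability p of a missing value at each of weeks 4, 8 and 12, the expected number is 20 × (1 − p)³:
   - p = 5%: 20 × 0.95³ = 17.1 (cumulative loss 14%)
   - p = 10%: 20 × 0.90³ = 14.6 (27%)
   - p = 15%: 20 × 0.85³ = 12.3 (39%)
   - p = 20%: 20 × 0.80³ = 10.2 (49%)

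3. **People left, total dropout d.** 20 × (1 − d): d = 10% gives 18; d = 20% gives 16; d = 30% gives 14; d = 40% gives 12.

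4. **Values thrown away.** Suppose six people stop, two after each of baseline, week 4 and week 8. They have given 2×1 + 2×2 + 2×3 = 12 values per outcome. The other 14 have given 14 × 4 = 56. Of 68 collected values, 12 are discarded.

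5. **Possible bias in a mean change.** Completer mean minus all-participant mean equals the fraction who stop times the difference in mean change between stayers and stoppers. If 15 stayers change by −1.0 kg and 5 stoppers would change by +2.0 kg, the completer mean is −1.0 kg and the mean for all 20 is (15 × −1.0 + 5 × 2.0)/20 = −0.25 kg, a gap of 0.25 × 3.0 = 0.75 kg. With the same 3.0 kg difference, the gap is 0.30 kg if 10% stop and 0.60 kg if 20% stop. If stayers and stoppers do not differ, it is zero.

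6. **Simulation.** 4000 runs per setting, 20 people, four times, true mean change zero, between-person baseline SD 1, all inputs assumed:
   - Dropout unrelated to outcome: 14.1 completers on average, completer change 0.00. Only participants were lost.
   - Dropout likelier in people not improving, at three strengths: 15.1, 14.3 and 13.3 completers, with spurious improvement of 0.09, 0.20 and 0.31. Friedman's test rejected in 5.0%, 6.95% and 10.9% of runs, against 4.3% with full data.
   - A fit with participant effects to all available data cut the bias to 0.03, 0.07 and 0.11. It allowed each person a level but not a slope, so some bias remained.

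**The case against.** Several stronger readings are tempting, and the documents do not support them.

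- A reader might infer that all Aim 2 measurement depends on staying in the intervention. That is documented for six of nine outcomes. For the three questionnaires the plan is silent on delivery at follow-up, and someone who stops logging but answers them stays in those tests. Equally, someone who stops coaching but keeps logging still supplies the six.
- A reader might infer that people who stop vanish from the study's results. They still count in the Aim 1 percentage dropped, and sample characteristics and frailty are summarised descriptively. The loss is confined to the Aim 2 tests, outcome by outcome.
- A reader might take the tilt towards benefit as established. The documents do not say who stops or why, and the one example given for missing data is forgetting to record.
- A reader might infer that these changes will set the effect size of a later trial. II.E says only that the study will help identify limitations to consider for a larger multisite trial.

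It is also fair that exclusion is the default of the named test rather than a rule the plan states, and that the plan does not define how daily records become a week 4, 8 or 12 value. A few unlogged days need not empty a time point. Nor is an available-data analysis a full cure: a person with baseline only says nothing about change, and a mixed model relies on missingness being explained by observed data. Choosing it over a rank-based method at this sample size is partly preference.

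These points limit the scope and make the bias conditional. They do not supply an analysis for incomplete participants or a route to later values for the six outcomes.

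**Conclusion.** The point holds in this limited form. Followed as written, the plan removes from each Aim 2 test anyone missing one of the four values, along with what that person had already given, and nothing in the missing-data text overrides this. For six outcomes, stopping the app ends the only described source of data; for the questionnaires, follow-up delivery is a gap in the text.

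Under the assumed rates the tests would rest on roughly 10 to 18 of 20 people. The direction of any bias depends on who stops: too favourable if they do worse than those who stay, and loss of precision alone if stopping is unrelated to outcome. The kilogram and simulation figures illustrate the mechanism and do not predict this study. Aim 2 is secondary in a feasibility study, so the primary outcomes are not threatened by this, but the change is worth making because it is cheap.

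**What to change.** - **II.D:** distinguish stopping the app or coaching from withdrawing consent. State that questionnaires, weight and blood pressure will be sought remotely at weeks 4, 8 and 12, using the supplied devices, from anyone who stops but does not withdraw consent.
- **II.F, analysis:** base the Aim 2 change estimates on all enrolled participants with any Aim 2 data, using a method that keeps incomplete participants. A mixed model with time as a factor would do this; the Skillings-Mack extension of Friedman's test is a rank-based alternative for the test.
- **II.F, reporting:** keep Friedman's test on complete cases as a supporting result with its n stated, and report n at each time point for each outcome.

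The cost is one procedure paragraph, a few analysis lines and a few extra remote contacts by the existing research assistant; no new staff or devices are needed. Some people who stop will decline. The available-data analysis reduces bias but does not remove it if missingness depends on values nobody observed, which is why the extra measurement matters as well as the change of method.

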Official Title:	The Use of a Consumer-Based mHealth Dietary App and Health Coaching with Kidney Transplant Recipients Study Information
NCT Number:	NCT05151445
Document Name:	Study Protocol and Statistical analysis Plan
Document Date:	05/05/2021

Study/Project Title: The Use of a Consumer-Based mHealth Dietary App and Health Coaching with Kidney Transplant Recipients

I. Objectives

The purpose of the study is to test the feasibility mHealth dietary app + health coaching for improving primary outcomes (recruitment, retention, and adherence) and secondary outcomes (perceived stress [Perceived Stress Scale], exercise self-efficacy[Exercise Self-efficacy Scale], vegetable intake [Fruit, Vegetables, and Fiber Screen] fat intake [Lose-it Premium database], carbohydrate intake [Lose-it Premium database], weight, blood pressure [Wi-Fi weight scale using the Lose-it Premium database], heart rate [Wi-Fi blood pressure cuff using the Lose-it Premium database], and the minutes of physical activity per day [Lose-it Premium database])

Background and Rationale Weight gain and obesity are common after kidney transplant, often leading to the development of cardiovascular disease, post-transplant diabetes, and death.¹ The increase in weight gain during the first year after transplant is associated with the use of immunosuppressive medications, and changes in lifestyle, such as dietary intake and insufficient physical activity. Moreover, weight gain is affected by factors such as, age, sex, race, and stress.² Evidence indicates that kidney transplant recipients who gain less weight after transplant are physically active, consume fewer carbohydrates, consume more vegetables, and experienced less stress.³ Further, limiting dietary fat and increasing post-kidney energy expenditures aid in preventing early insulin resistance and cardiovascular disease.^{4 5}

However, few studies have tested dietary and physical activity interventions using real-time mobile health applications (mHealth) to enhance lifestyle self-management of care with kidney transplant recipients.⁶

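### The primary adherence outcome has no fixed denominator and no rule for participants who stop, so it would describe only those still taking part

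*Combined protocol and SAP*

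**What the plan says.** - Section I (Objectives) sets out to test feasibility for "improving primary outcomes (recruitment, retention, and adherence", so adherence is one of three primary outcomes.
- II.C (Aim 1) defines adherence only as "percent to adhere to logging daily dietary intake and physical activity", which "will be recorded continuously each day by the “Lose-It” app". It does not say what counts as a logged day or what the percentage is taken over. Retention is a separate measure, the percentage dropped.
- II.D gives the logging period as an instruction to participants: "The participants will be trained to enter their dietary intake and physical activity daily for 12-weeks".
- The Background and Rationale in section I plans to "recruit a sample (N = 20) of post-kidney transplant recipients (age 18 and above"), and promises: "We will assess changes over time for the primary outcome and secondary outcomes from baseline to 4, 8, and 12 weeks".
- II.F (Aim 1) summarises adherence by means and standard deviations and tests the baseline to 3-month difference with the Wilcoxon signed-rank test. It names no analysis set, gives no analysis at weeks 4 or 8, and has no rule for people who stop.
- II.F (Missing Data) says: "We will carefully record and code various reasons for missing data (e.g., participants forgot to record data into the" app. Beyond coding reasons it commits only to looking at the pattern. It is not tied to either aim.

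**The concern.** A blank day in the app means two different things. For fat intake, carbohydrate intake and activity minutes (Aim 2), it is a missing value. For adherence (Aim 1), it is an observed failure to log. II.F does not separate the two uses, and its one example of missing data is the event that the adherence outcome exists to count.

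There are two routes by which failures can leave the calculation:

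1. **Days after stopping.** A signed-rank test uses only participants who have both values. With no rule that scores a stopped participant, anyone without a 3-month value is left out.
2. **Forgotten days.** If these are coded as missing for adherence as well, they leave the denominator.

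II.E says the study is meant to identify limitations ahead of a larger multisite trial. An adherence figure that describes only those still taking part would be a weak guide for that trial.

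**Working it through.** The documents state no expected adherence, dropout rate or feasibility threshold, so there is no planned figure to reproduce. The check asks how far the figure moves with the denominator.

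**Inputs from the documents**
- Enrolled: 20 (section I, Background and Rationale).
- Logging period: 12 weeks (II.D), so 12 × 7 = 84 days each and 20 × 84 = 1,680 planned person-days.

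**Assumed inputs**
- Logging while on study, p: 80% (also 60%).
- Number stopping, d: 5 (range 2 to 8).
- Day of stopping, s: 28 (also 42).

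**Formulas**
- Days logged = p × [(20 − d) × 84 + d × s]
- All-enrolled adherence = days logged / 1,680
- On-study adherence = days logged / [(20 − d) × 84 + d × s] = p

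**Main illustration (p = 80%, d = 5, s = 28)**
- Days logged: 15 × 84 × 0.8 + 5 × 28 × 0.8 = 1,008 + 112 = 1,120.
- On-study days: 1,260 + 140 = 1,400, and 1,120/1,400 = 80%.
- All planned days: 1,120/1,680 = 66.7%, a gap of 13.3 points.
- Weeks 9-12: 15 × 28 × 0.8 = 336 days logged. On study, 336/420 = 80%. All enrolled, 336/560 = 60%.

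**Range at p = 80%**

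| Stopping, of 20 | On study | All enrolled, stop at day 28 | All enrolled, stop at day 42 |
|---|---|---|---|
| 2 | 80% | 74.7% | 76.0% |
| 4 | 80% | 69.3% | 72.0% |
| 6 | 80% | 64.0% | 68.0% |
| 8 | 80% | 58.7% | not computed |

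At p = 60%, the all-enrolled figure runs from 57.0% (2 stopping at day 42) to 48.0% (6 stopping at day 28), against 60% on study.

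**Forgotten days, shown separately.** In the main illustration, 1,400 − 1,120 = 280 on-study days are unlogged. Removing half of them as forgotten gives 1,120/1,260 = 88.9%. Removing all gives 1,120/1,120 = 100%, whatever the true logging rate.

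**Baseline comparison.** II.D sets up the app at the baseline session (Session 1), so no app logging exists before it. The paired test in II.F has no baseline adherence value to use.

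**The case against.** The strongest reply is that II.F never says forgotten days leave the adherence calculation. The missing-data sentence follows Aim 2 and frailty, and its example is legitimate for the app-recorded Aim 2 outcomes. Coding why a day is blank requires first identifying it as unlogged. Daily logging for 12 weeks suggests days logged over days expected, and removing every unlogged day would give a meaningless 100%. This stands in part. A reader might infer that the plan excludes forgotten days, but the documents do not say so. That route is only a possibility, and the gap of 80% against 67% comes wholly from days after stopping.

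A reader might also infer that the reported figure rises as more people leave. The arithmetic does not show that: the on-study figure stays at 80% and only the gap grows. Nor do the documents show that those who stop log less while taking part. The illustration gives them the same 80%.

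Retention is reported separately, so dropout is not hidden, and on-study adherence beside retention is a legitimate description. That also stands, but as a choice to be stated. Retention does not reveal forgotten days, and it does not turn a figure for those remaining into one for all enrolled.

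Finally, no feasibility threshold is given, so no stated decision would change. That limits the consequence but does not supply the missing rule.

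**Conclusion.** The point holds in this form: II.F sets no denominator for a primary outcome, does not confine its missing-data example to Aim 2, and uses a paired comparison with no rule for those who stop. Followed as written, the 3-month adherence analysis is restricted to people who still have a 3-month value. Exclusion of forgotten days is possible but not stated.

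The size cannot be derived from the documents. Under the assumed 80% logging on study, the gap is 13.3 points over 12 weeks and 20 points in weeks 9-12 with 5 of 20 stopping at day 28. Over 12 weeks it runs from 5.3 points (80 − 74.7) with 2 stopping then to 21.3 points (80 − 58.7) with 8. The change should be made because the same logs could be reported quite differently and the plan does not say which figure is meant.

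**What to change.** In II.F:

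- Define adherence as days logged divided by the 84 planned days after the baseline session, for every enrolled participant.
- Define a logged day so that a day with no exercise can be recorded as zero activity and is not scored as a failure to log.
- Count unlogged days, including all days after stopping, as not logged.
- Report adherence for weeks 1-4, 5-8 and 9-12 with all enrolled participants as denominator, in place of the baseline comparison. This also matches the week 4, 8 and 12 assessments promised in section I.
- Give on-study adherence beside retention as a secondary description.
- Show days lost to verified technical or sync failure separately.
- Limit missing-data coding of unlogged days to the Aim 2 app-recorded outcomes.

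The cost is a short paragraph in II.F and an instruction at the baseline session on entering zero activity. The app already records logging each day and reasons for blank days are already to be coded, so no new measurement is needed. The downside is a less favourable adherence figure. Days lost to technical failure also count against the main figure, which is why they should be shown separately.
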